Study participants will include non-pregnant women aged 18 years or older scheduled to have unilateral DIEP flap breast reconstruction. Patients will be required to have an ASA physical status classification of 1, 2, or 3. Patients will be excluded if they have a concurrent or recent medical condition that could interfere with study participation, including history of hepatitis, alcohol/substance abuse, uncontrolled psychiatric disorders, known allergy, or contraindication to amide-type local anesthetics, opioids, or propofol. Patients will also be excluded if they have a body weight of less than 50 kg, have participated in another study involving an investigational medication within the prior 30 days, or are taking analgesics (ie, nonsteroidal anti-inflammatory drugs, acetaminophen, or opioids), antidepressants, or glucocorticoids within the 3 days before surgery.

Describe the control population

Group 3 of our study will compromise the control group for our study. Patients in this arm will receive .25% bupivacaine without epinephrine injected using ultrasound guidance in between the internal oblique and transversus abdominis muscles as well as along incisional lines. This form of local wound infiltration is the current standard of care for post-operative pain management for DIEP reconstructions of the breast.

Support the likelihood of recruiting the number of subjects required

Evidence from our Breast Reconstruction database using data transferred from Epic/Clarity, in 2014 show fifty four unilateral DIEP breast reconstructions were performed and in 2013 sixty six unilateral DIEP breast reconstructions were performed.

Project Design and Protocol

All patients meeting the inclusion criteria will be randomized using a blocked randomization technique, stratifying patients by the timing of the procedure, and it will be employed to allocate patients in equal numbers to each group. The randomization will be created using the plan procedure within SAS software (version 9.3 or higher; Cary, NC).. Patients will be assigned to one of three groups: Group 1 -DepoBupivicaine Injection; Group 2- OnQ catheter placement, and the control Group 3- 0.25 % Bupivicaine injection.

Bupivacaine is a commonly utilized medicaiton for post-operative pain control with a favorable side-effect profile. The dosages of medications given in the study are within safe limits.

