Our primary endpoints will be postoperative pain as measured by total postoperative morphine or hydromorphone utilization from a patient controlled anesthesia pump (PCA) and pain scores on visual analog scale (VAS). The VAS will be measured while the patient is at rest (VAS-R) and after the patient is asked to cough (VAS-C). For each patient, the area under the curve (AUC) of the VAS-R will be calculated. Morphine usage will be tracked by patient controlled analgesia (PCA) dispensed. Using the medication chart, any rescue medications beyond the PCA will also be recorded. Patients will be interviewed and asked to rate their postoperative pain on a 10-point scale with 0 being no pain and 10 being the most pain. Another variables recorded will include incidents of nausea or vomiting, time to first ambulation, and time to first liquid and solid oral intake. All measurements for variables were obtained at 6 hrs, 12 hrs, 24 hrs, 48 hrs, 72 hrs. Nursing staff on our designated breast reconstruction floor will be instructed on how to interview patients and collect data for the 6 and 12 hour timepoints. This information will be stored on Epic EMR in a stardard note and nurses will be given a smart text to use in order to appropriately ascertain all information. The 24, 48, and 72 hour time points will be collected by the co-investigators. Any pain medications given by PCA, IV or PO will recorded and converted to morphine as diagramed below:

Drug	Parenteral (mg)	Oral (mg)
Morphine	10	30
Hydromorphone	1.5	7.5
Oxycodone	NA	20
Hydrocodone	NA	30-45
Oxymorphone	1	10
Meperidine	75	300
Codeine	130	200

Equianalgesic Potency Conversion TABLE A

Discuss limitations and difficulties

The limitations of our study include potential confounding pain from the mastectomy site, the subjectivity in patient perception of pain, and differences in patient threshold to request patient- controlled anesthesia and oral narcotics

Provide the tentative schedule for completion

Our schedule for the study will be 6 months continuous enrollment and experimentation from September to February, or until our groups are filled.

Data collection

The data fields will be: Birth date, sex, type of surgery, utilization of mesh, number of mg on PCA, VAS at rest and VAS with cough, number of rescue pain medications given, number of incidents of nausea/vomiting, time to first ambulation, time to first liquid and solid intake post surgery.

Planned Data Analysis

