The data will be examined with an analysis of variance (ANOVA) procedure with repeated measures. The design will have one between factor, (group (3), and one within factor, time (6). The analysis will test for a group effect, a time effect and a group by time interaction. We anticipate that the three groups will be comparable at the start. This implies the likelihood of a significant interaction term. If this happens, our primary analysis will focus on the ANOVA for the 72-hour time point. This will show us if a differential effect has occurred. All assumptions of the test will be examined and data transformations or nonparametric methods used if indicated.

We will not be utilizing QHS, rather, one of the plastic surgery residents, [name], will serve as our statistician.

Sample Size Justification

We propose to randomly assign individuals recruited during the recruitment period into 3 equal groups. With three groups this translates to a difference between groups of 5 for total morphine used on day 3 and 0.7 for the VAS. This assumes standard deviations of 4.9 for morphine and 0.7 for VAS. Effects of these sizes represent clinically important differences in the range that we believe will happen.

References:

- Feng LJ. Painless abdominoplasty: the efficacy of combined intercostal and pararectus blocks in reducing postoperative pain and recovery time. Plast Reconstr Surg. 2010 Nov;126(5):1723-32.

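### Randomisation is stratified by timing of the procedure, but neither planned ANOVA includes timing; if timing predicts outcome, the group tests are conservative and give up some precision.

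*Combined protocol and SAP*

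**What the plan says.** Under Project Design and Protocol, patients are allocated by blocked randomisation in equal numbers to three groups, "stratifying patients by the timing of the procedure". The strata are not defined or counted.

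The Planned Data Analysis section specifies a repeated-measures ANOVA: "The design will have one between factor, (group (3), and one within factor, time (6". It continues: "The analysis will test for a group effect, a time effect and a group by time interaction". The plan expects a significant interaction, in which case "our primary analysis will focus on the ANOVA for the 72-hour time point". No stratum or covariate is named for either analysis. The only flexibility offered is transformation or nonparametric methods.

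The Data collection section begins "The data fields will be: Birth date, sex, type of surgery, utilization of mesh, number of mg on PCA" and goes on to pain scores, rescue medication and recovery measures. Timing of the procedure is not named among them.

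**The concern.** The word time in the analysis section could be mistaken for the stratification factor. It is the within-patient factor, that is, hours after surgery. Procedure timing is a characteristic of the patient's operation and appears in no analysis.

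Stratified blocking balances timing across the three groups, so timing adds little or nothing to the true variability of a group comparison. An ANOVA on group alone still counts the difference between timing strata as residual error. If timing is prognostic, the standard error is overstated, the nominal 5% test rejects too rarely, and the benefit of stratifying is not collected.

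This affects the two between-patient tests: the overall group effect and the 72-hour ANOVA that the plan expects to become primary. A timing effect that is constant over the postoperative period cancels in within-patient contrasts, so the group-by-time test is unchanged by it.

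**Working it through.** **Inputs from the documents.** Sample Size Justification gives a difference of 5 for day-3 morphine and 0.7 for VAS, and "This assumes standard deviations of 4.9 for morphine and 0.7 for VAS". The standardised difference for morphine is d = 5/4.9 = 1.02. No sample size, alpha or power is stated, so there is no plan figure to reproduce.

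**Range for the sample size.** The recruitment section says that records "in 2014 show fifty four unilateral DIEP breast reconstructions were performed and in 2013 sixty six unilateral DIEP breast reconstructions were performed". The schedule is "6 months continuous enrollment and experimentation from September to February, or until our groups are filled". Half a year at those rates is 54/2 = 27 to 66/2 = 33 patients, or 9 to 11 per group if every patient enrols and enrolment stops at six months. Sizes of 16 and 20 per group are added as assumptions.

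**Other assumptions.** Two-sided alpha 0.05; two equal timing strata balanced within groups; one group shifted by d; total within-group SD fixed at the plan's value; R² is the share of that variance explained by timing.

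**Meaning of R².** With two equal strata, the gap between timing means is 2 × √R² × SD. For R² = 0.10 on morphine this is 2 × 0.316 × 4.9 = 3.1.

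| R² | Gap, morphine | Gap, VAS |
|---|---|---|
| 0.02 | 1.4 | 0.20 |
| 0.05 | 2.2 | 0.31 |
| 0.10 | 3.1 | 0.44 |

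**Formulas** (n per group, N = 3n, sums of squares divided by 1 − R²):

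- Group sum of squares: noncentral chi-square, 2 df, noncentrality (2/3)·n·d²/(1 − R²). For n = 10 and R² = 0.10 this is 6.94/0.90 = 7.71.
- Error sum of squares without timing: noncentral chi-square, N − 3 df, noncentrality N·R²/(1 − R²). Power and size follow by numerical integration against the F(2, N − 3) critical value.
- With timing: noncentral F on 2 and N − 4 df, with the same group noncentrality.
- Standard-error inflation without timing: √[1 + (N/(N − 3))·R²/(1 − R²)]. For N = 30 and R² = 0.10 this is √(1 + 1.111 × 0.111) = 1.06.

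**Size and standard error without timing.**

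| R² | Actual size of nominal 5% test | Standard error inflated by about |
|---|---|---|
| 0 | 5.0% | 0% |
| 0.02 | 4.7% | 1% |
| 0.05 | 4.3% | 3% |
| 0.10 | 3.6% | 6% |

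**Power (%), without vs with timing.**

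| n per group | R² 0 | R² 0.02 | R² 0.05 | R² 0.10 |
|---|---|---|---|---|
| 9 | 54.6 vs 54.3 | 54.3 vs 55.2 | 53.9 vs 56.6 | 53.3 vs 59.0 |
| 10 | 59.9 vs 59.7 | 59.8 vs 60.7 | 59.5 vs 62.1 | 59.1 vs 64.6 |
| 11 | 64.9 vs 64.7 | 64.8 vs 65.7 | 64.6 vs 67.1 | 64.3 vs 69.6 |
| 16 | 83.0 vs 83.0 | 83.1 vs 83.8 | 83.3 vs 85.0 | 83.6 vs 86.9 |
| 20 | 91.2 vs 91.1 | 91.3 vs 91.7 | 91.5 vs 92.5 | 91.9 vs 93.8 |

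Power without timing hardly moves along each row, so the omission takes nothing from the plan's own sizing; it leaves a gain uncollected. Gains above those shown need a timing gap close to or above the target effects: R² = 0.20 already means gaps of 4.4 and 0.63, against targets of 5 and 0.7.

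**Check with imperfect balance.** The check simulated 20,000 trials per cell with random stratum membership, permuted blocks of 6 (assumed), incomplete last blocks and R² = 0.10. At N = 30 it gave 59.2 vs 64.1% with strata 50:50 and 58.4 vs 63.7% with strata 25:75. At N = 60 it gave 91.4 vs 93.5% and 91.6 vs 93.7%. Size without timing was 3.6 to 3.9% over the cells run (N = 30, 48 and 60); with timing it was 4.8 to 5.3%.

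These figures are for the 72-hour ANOVA. With complete data the overall group test is the same ANOVA on patient means, for which the plan gives no effect or SD.

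**The case against.** The strongest objection is that the improvement is cheap only if there are few strata, and the protocol does not say how many there are. With many small strata, incomplete blocks cost balance as well as degrees of freedom. In simulations at N = 30 with no timing effect, power without vs with timing was 58.6 vs 57.5% with four strata and 59.6 vs 55.5% with six. With four strata, adjustment roughly broke even near R² = 0.02. This stands as a limit on the calculation. Six strata would, however, mean reading timing as something like calendar month over the six-month schedule. That is a strained reading, and the loss nearly disappears at N = 60. It is a reason to define the strata first, and not a reason to leave timing out.

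The second objection is that the gain is conditional and mostly small, with no bias and no inflated type I error. That is correct, and it limits the point to a worthwhile improvement.

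Third, the stratum must already be known at allocation, so its absence from the data-field list is a small matter. That is also correct; it needs only to be carried into the analysis dataset.

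Finally, adding a factor to the ANOVAs does not cover the nonparametric fallback. That is a fair addition and is included in the fix.

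**Conclusion.** The concern holds. The trial stratifies on procedure timing and then analyses as if it had not. If timing is prognostic, the between-patient group tests are conservative. With two balanced strata, including timing gains about 0 to 3 points of power for R² up to 0.05 and about 2 to 6 points at R² = 0.10, with the larger gains in the smaller trials. If timing is not prognostic, nothing is forgone by leaving it out.

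Validity is not at risk. The magnitudes rest on assumed values for alpha, sample size, number of strata and R². The documents report no outcomes by timing, so these are illustrations and not expected values.

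**What to change.** 1. Define the timing strata in the protocol, keep them few, and add the stratum to the data-field list.
2. Include the stratum as a between-patient factor in both the repeated-measures ANOVA and the 72-hour ANOVA. State this before any outcome is compared by group.
3. If a nonparametric method replaces the ANOVA, use a version stratified by timing.

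The cost is one data field, already known at randomisation, and k − 1 error degrees of freedom for k strata. With two balanced strata and no timing effect, the power lost is 0.24, 0.20, 0.16, 0.06 and 0.03 points at 9, 10, 11, 16 and 20 per group. It is up to about 0.5 points at 10 per group with incomplete blocks. With two balanced strata, including timing pays once R² exceeds about 0.004 at 9 to 10 per group (a morphine gap of 2 × √0.004 × 4.9 = 0.6), or about 0.001 at 20 per group.

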For patients assigned to the Group 2 (OnQ) the surgeons will be given an instruction sheet with specific placement of catheter (See Bulter et al). All patients in the group will have two ON-Q soaker catheters installed into the abdominal donor site before donor-site closure. The catheters will be inserted through 3-mm stab incisions in the suprapubic area and 3 cm caudal to the donor-site incision. One catheter will be placed directly in the plane between the internal oblique and the transversus abdominus (see Hebbard et al), and the second catheter will be placed subcutaneously, superficial to the anterior rectus sheath along the superior aspect of the donor site (Figure 1). At the conclusion of surgery, a 4-ml/hour infusion 0.25% Bupivicaine % solution will be delivered continuously by the continuous infusion

pump system (2 ml/hour through each catheter). All patients will have two closedsuction drains placed at the inferior aspect of the donor site, oriented horizontally and remote from the any infusion catheters.

Patients assigned to the control Group 3 (0.25 % Bupivicaine) will be given 0.25% bupivacaine without epinephrine. A dose of 2mg/kg will be given. Thus, a 80 kg patient will be given 80 cc of 0.25% Bupivacaine . The infiltration technique for the Maracine will be identical to the EXPERAL injection whereby 20 cc of will injected with a 25-gauge needle on either side of the suture line (Figure 2 and Figure 3) directly into the fascia above the muscle layer. The injections will be done in between internal oblique and transversus abdominus muscles as determined via ultrasound. Another 20 cc of will be injected on the outside edge of the surgical site where the sensory nerves branch up from the fascia to the skin flap (Figure 3). The final 20 cc will be injected along the length of the incision where skin will be anchored down; care will be taken to inject the product near the ileoinguinal nerve to ensure appropriate analgesic coverage (Figure 4). Once again, the 0.25% Bupivacaine will be injected directly into the fascia above the muscle layer. All patients will have two closed-suction drains placed at the inferior aspect of the donor site remote from the any infusion catheters and oriented horizontally.

[figure not shown]

Figure 1. A. OnQ catheter *in vivo* prior to closure of open abdomen (See Haller et al) B. Schematic of OnQ catheter place in a plane above the Tranversus Abdominus (TA) (see Hebbard et al)

[figure not shown]

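### The planned ANOVA has group as its only between-patient factor, leaving out procedure timing (the randomisation stratum) and age (available from birth date): a possible loss of precision, not a bias.

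*Combined protocol and SAP*

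**What the plan says.** Under Planned Data Analysis, the protocol states: "The data will be examined with an analysis of variance (ANOVA) procedure with repeated measures". It then defines the model: "The design will have one between factor, (group (3), and one within factor, time (6". If the group-by-time interaction is significant, "our primary analysis will focus on the ANOVA for the 72-hour time point". No covariate or stratum term appears in either analysis.

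Elsewhere the document names two pre-randomisation variables that could enter the model:

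- **Procedure timing.** Project Design and Protocol describes blocked randomisation "stratifying patients by the timing of the procedure". The number of timing levels is not given.
- **Age.** Data collection begins "The data fields will be: Birth date, sex, type of surgery, utilization of mesh, number of mg on PCA", so age can be derived for every patient.

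Body weight has a different status. It must be known to apply the entry criterion ("Patients will also be excluded if they have a body weight of less than 50 kg") and to dose Group 3 ("A dose of 2mg/kg will be given"), but it is not in the list of data fields.

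**The concern.** When randomisation is stratified, the groups are balanced on the stratum by design. If the stratum is then left out of the model, the variance it explains stays in the residual. The standard error tends to be too large and the test conservative. The same holds, without the design balance, for any other baseline variable related to outcome: its share of the variance is counted as noise.

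The plan schedules no baseline pain or opioid value, since measurement starts at 6 hours. Timing and age are therefore among the few pre-randomisation variables available for adjustment. At stake is the width of the intervals for the group comparisons, including pump versus DepoFoam. There is also a prespecification issue: if covariates are not named now, any later adjustment would be open to choice after the data are seen.

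**Working it through.** **Inputs from the document.** Sample Size Justification gives a difference of 5 and SD of 4.9 for morphine on day 3, and 0.7 and 0.7 for VAS. Allocation is to three equal groups.

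**Not in the document.** There is no sample size, alpha, power, or correlation of age or timing with outcome, so there is no stated power figure to reproduce. Assumptions: two-sided alpha 5%; a linear age effect with correlation r to the outcome, varied from 0 to 0.5; and two illustrative sizes.

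- *10 per group.* Annual volumes of 66 and 54 give 33 and 27 cases in the planned 6 months, or 11 and 9 per group before exclusions and refusals.
- *17 per group.* This is just above the 16 implied for 80% pairwise power by the plan's own figures: 2 × (1.960 + 0.842)² × 4.9²/5² = 15.1, rounded up.

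**Unadjusted.** The pairwise contrast uses the pooled error from three groups. Noncentrality = (5/4.9) × √(n/2), with df = 3n − 3.

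- n = 10: 1.020 × √5 = 2.282, df 27, power 59.5%.
- n = 17: 1.020 × √8.5 = 2.975, df 48, power 83.0%.

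**Adjusted for age only.** Divide the noncentrality by √[(1 − r²) × (1 + 1/(3n − 5))], with df = 3n − 4. The second factor is the average inflation from chance imbalance in the covariate: 1.040 at n = 10 and 1.022 at n = 17. Example at n = 10, r = 0.4: 2.282/√(0.84 × 1.04) = 2.441, df 26, power 65.2%.

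| r (assumed) | Power, 10 per group | Power, 17 per group |
|---|---|---|
| unadjusted | 59.5% | 83.0% |
| 0 | 57.7% | 82.2% |
| 0.2 | 59.4% | 83.7% |
| 0.3 | 61.7% | 85.6% |
| 0.4 | 65.2% | 88.2% |
| 0.5 | 70.1% | 91.4% |

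The adjusted and unadjusted analyses break even at r of about 0.20 (10 per group) and 0.15 (17 per group).

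**VAS.** The standardised difference is 0.7/0.7 = 1.00 instead of 1.02, so the pattern is the same from a slightly lower start: 57.8% and 81.5% unadjusted.

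**Adding weight as a second covariate (opioid model).** The inflation becomes 1 + 2/(3n − 6), with df = 3n − 5. At 10 per group, power is 55.9% at joint R² = 0, 58.0% at 0.05 and 59.8% at 0.09; break-even is about 0.08. At 17 per group, power is 81.3% at R² = 0, and break-even is about 0.04.

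**The stratum term.** Blocking holds timing close to balance, so its cost is mainly lost degrees of freedom. At 10 per group, losing two error df with no imbalance inflation moves power only from 59.5% to 59.2%. The gain cannot be computed, because the document gives no figure for how timing relates to outcome.

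**Where the gain falls.** It applies to the group effect and to the 72-hour comparison. A main effect of age or timing does not reduce the within-patient error used to test group by time.

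**The case against.** The strongest reply is that a group-only ANOVA is a legitimate choice. Randomisation makes it valid, and chance imbalance in age or weight is already allowed for in its standard error. That stands. A reader might infer that imbalance biases the comparison, or that adjustment would remove it. Neither follows: adjustment corrects only the linear part, for the covariates included.

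Second, nothing in the document says that age or weight predicts opioid use or VAS. The limitations it lists are mastectomy-site pain, subjective perception of pain, and differing thresholds for requesting analgesia. This also stands, and it is why r is shown from 0 upward.

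Third, a reader might infer that weight must be in the opioid model, because the endpoint is in mg and only Group 3 is dosed by weight. The document does not support that. Weight is not a data field, no relation to outcome is shown, and its slope might differ by group. With age and weight together at 10 per group, power falls unless they jointly explain about 8% of the variance.

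Fourth, calling this a very small trial goes beyond the text. No sample size is stated, and enrolment may continue until the groups are filled. The missing sample size, alpha and power are a larger gap than the missing covariates.

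What survives is narrower. The design singles out procedure timing and the model omits it; age is available from a field already collected, and using it risks little.

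**Conclusion.** The point holds as a matter of efficiency and prespecification. The stated model omits the randomisation stratum and a baseline variable already collected, so any variation they explain stays in the error term. It is not an error of validity and not a source of bias.

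For age alone, the effect on pairwise power runs from −1.8 points (r = 0) to +10.6 points (r = 0.5) at an assumed 10 per group, and from −0.8 to +8.4 points at an assumed 17. These figures rest on the plan's difference and SD, two-sided 5%, assumed group sizes and an assumed correlation. The benefit of the stratum term is not quantified. Confidence is moderate: the omission is plain in the text, but the size of the gain is not known.

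**What to change.** Add one sentence to Planned Data Analysis, before any outcome data are examined: each group comparison of opioid use and of VAS, including the 72-hour comparison, will include the randomisation stratum (procedure timing) and age (continuous, from birth date) as fixed terms. Carry the stratum from the randomisation list into the analysis file, since timing is not among the listed data fields. The deadline should be tied to examination of outcomes, not to unmasking, because the document describes no blinding.

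Weight is optional, for the opioid model only, and only if it is added to the data fields. Do not add a surgeon effect: surgeon is not a data field, and the number of surgeons is not given.

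The cost is one sentence and no extra patients. Each term uses one error degree of freedom (for the stratum, its number of levels less one) and brings a small variance inflation. If age is not prognostic, including it loses under 2 points of power at either size. Adding weight raises the break-even to a joint R² of about 0.08 at 10 per group and 0.04 at 17, which is the reason to keep the list short.

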We would like to compare Clevleland Clinic Foundation's experience with unilateral DIEP flap breast reconstruction to determine if postoperive pain management is improved

with either Depobupivicaine, a local infusion anesthetic pump as comapred to patients given standaad analgesic. We would like to conduct this study to better serve DIEP surgery patients

In a IRB approved pilot study performed by [name], at Henry Ford Medical Center in Detroit, MI in 2014, depoFoam Bupivicaine was compared to Bupivicane alone in patient undergoing breast reconstruction with transverse rectus abdonius muscle (TRAM) or abdominoplasty procedures.

The primary endpoints were postoperative pain as measured by total postoperative morphine or hydromorphone utilization in a patient controlled analgesia (PCA) and pain scores on visual analog scale (VAS). The VAS was measured while the patients were at rest (VAS-R) and after the patient was asked to cough (VAS-C). Morphine usage was tracked by amount dispensed by the PCA pump. Using the medication chart any rescue medications beyond the PCA usage was also recorded. Patients were also interviewed and asked to rate their postoperative pain on a 10-point scale with 0 being no pain and 10 being the most pain. Other variables recorded were incidents of nausea or vomiting, time to first ambulation, and time to first liquid and solid oral intake. All variable measurements were obtained at 30 minutes, 6 hours, 12 hours, 24 hours, 48 hours, and 72 hours postoperatively

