A total of twenty patients were randomized into Depofoam bupivacaine group (Exparel, n=15), and continuous infusion pump system (On-Q, n=5) after undergoing abdominoplasty or TRAM flaps. The Exparel group demonstrated higher morphine usage at the 30 minute time point compared to the On-Q group (5.2 mg vs 1.2mg), but a significantly lower volume at all other time points when compared to the On-Q group (6.2 mg vs 16.42 mg at 6 hrs; 5.5 mg vs 14.8 mg at 12 hrs; 5.98 mg vs 14.9 mg at 24 hrs; 5.23 mg vs 11.63 mg at 48 hrs; 2.7 mg vs 12.65 mg at 72 hrs). The VAS scores for the On-Q group were higher at the earlier time points (up to 6 hours) when compared to Exparel group and relatively the same during the remainder of the study (Figure 1 and Figure 2). The remaining variables that were examined revealed that the Exparel group had more nausea and vomiting at earlier time points but that the same group was ambulating, drinking and eating solid food at earlier time points than the On-Q group.

From this pilot study we concluded that with the use of a depot form of bupivicaine (Exparel), more effective postsurgical pain control was achieved in patients undergoing abdominoplasty or TRAM flap reconstruction than those that used an indwelling fusion pump catherters (On–Q pump). Further studies are necessary to enroll more participants undergoing these specific procedures in which this type of post surgical pain control may be most effective.

Our goal in this study is to expand the finding based from our pilot study by observing only those that undergo breast reconstruction with a DIEP flap.

[figure not shown]
[figure not shown]

Figure 2

Subjects in the project

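### The ANOVA is written for six time levels but only five readings are scheduled, none at a start, and the interaction test that picks the primary analysis has no stated fallback

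*Combined protocol and SAP*

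**What the plan says.** Planned Data Analysis sets out a repeated-measures ANOVA: "The design will have one between factor, (group (3" levels) and "one within factor, time (6" levels), with tests of group, time and their interaction. It then reasons: "We anticipate that the three groups will be comparable at the start. This implies the likelihood of a significant interaction term". If the interaction is significant, the primary analysis becomes the ANOVA at 72 hours. The section does not say what is primary otherwise.

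Post-operative Protocol gives the schedule: "All measurements for variables were obtained at 6 hrs, 12 hrs, 24 hrs, 48 hrs, 72 hrs". It assigns the work to match. Nursing staff are to "collect data for the 6 and 12 hour timepoints", and "The 24, 48, and 72 hour time points will be collected by the co-investigators". Neither this section nor the field list under Data collection mentions a baseline, 30-minute or other starting reading.

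A six-reading schedule appears only in the pilot description under Significance: "All variable measurements were obtained at 30 minutes, 6 hours, 12 hours, 24 hours, 48 hours, and 72 hours postoperatively".

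**The concern.** The number of time levels in the model does not match the number of readings. The mismatch matters because the argument for the decision rule depends on a start. The groups are expected to be alike there and to diverge later, and the resulting interaction is used to select the primary analysis. Under Operative Technique both injections are given during surgery and the pump starts at its end, so the 6-hour reading already reflects treatment. Comparability at an unmeasured start does not tell us whether the five measured profiles are parallel.

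Two things are at stake. The premise behind the rule cannot be checked from the scheduled data. And the primary analysis depends on a significance test whose outcome is uncertain, with one branch left undefined.

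**Working it through.** **1. Count of readings.** The plan's figure is six levels. The schedule gives 6, 12, 24, 48 and 72 h, which is five. The staffing instructions give 2 (nurses) + 3 (co-investigators) = 5. Only the pilot schedule, with 30 minutes added, gives six. For 3 groups and T times, the interaction df are (3 − 1)(T − 1): 10 for T = 6 and 8 for T = 5. The within-patient error df are (N − 3)(T − 1): 5(N − 3) and 4(N − 3).

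**2. What the 30-minute reading contributes in the pilot morphine means** (Significance). Let d be On-Q minus Exparel, in mg:

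| Time | Exparel | On-Q | d |
|---|---|---|---|
| 30 min | 5.2 | 1.2 | −4.00 |
| 6 h | 6.2 | 16.42 | 10.22 |
| 12 h | 5.5 | 14.8 | 9.30 |
| 24 h | 5.98 | 14.9 | 8.92 |
| 48 h | 5.23 | 11.63 | 6.40 |
| 72 h | 2.7 | 12.65 | 9.95 |

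The two-group interaction sum of squares is proportional to Σ(d − mean d)².

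- Six readings: mean 40.79/6 = 6.798; sum 116.60 + 11.71 + 6.26 + 4.50 + 0.16 + 9.93 = 149.16.
- Five readings: mean 44.79/5 = 8.958; sum 1.593 + 0.117 + 0.001 + 6.543 + 0.984 = 9.24.
- Share lost: 1 − 9.24/149.16 = 93.8%. Dropping any other single reading leaves between 135 and 149.

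The pilot text gives no VAS figures, so this cannot be repeated for VAS.

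**3. How likely the trigger is to fire with five readings.** SD 4.9 is from Sample Size Justification. The remaining inputs are assumptions, because the documents do not give them: two-sided 0.05, compound symmetry with correlation ρ from 0.3 to 0.7, 15 to 20 patients per group, pilot differences in full or halved, and a profile for the control arm, which the pilot results do not report.

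Power comes from the noncentral F with λ = nS/[4.9²(1 − ρ)], where S is the sum of squared interaction effects over groups and times.

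- Control equal to an active arm: S = (2/3) × 9.238 = 6.159.
- Control midway between them: S = (1/2) × 9.238 = 4.619.
- Control equal to Exparel at 6 and 12 h and to On-Q from 24 h: centre each arm's profile on its own mean over time, taking Exparel as zero. The squares sum to 9.24 (On-Q) + 91.81 (control) = 101.05. Subtract 3 × 9.71 = 29.12 for the time means, which leaves S = 71.93.

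Halving the differences divides S by 4. Example: control equal to an active arm, n = 15, ρ = 0.5 gives λ = 15 × 6.159/(24.01 × 0.5) = 7.70 on 8 and 168 df, and power 44%.

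| Control arm (assumed) | Differences | Power, ρ = 0.5 | Power, ρ = 0.3 to 0.7 |
|---|---|---|---|
| Equal to an active arm | full | 44-58% | 31-84% |
| Equal to an active arm | half | 12-16% | 10-25% |
| Midway | full | 33-44% | 23-70% |
| Midway | half | 10-12% | 9-19% |
| Exparel to 12 h, On-Q from 24 h | full | about 100% | about 100% |
| Exparel to 12 h, On-Q from 24 h | half | 94-99% | 81-100% |

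With six readings and control equal to an active arm, power at ρ = 0.5 is about 100% for full and 98-99.8% for half differences.

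**The case against.** The strongest reply is that this is one wrong digit. The same ANOVA can be fitted with five levels, the plan never says that the sixth level is a starting reading, and starting comparability may simply mean that randomisation balances the groups. All of that is fair, and the link to the pilot's 30-minute reading is an inference. It does not rescue the rule. Balance before treatment does not imply an interaction among readings taken from 6 hours on, and the branch without a significant interaction stays undefined.

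Three stronger readings are tempting, and the documents support none of them.

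- *That the interaction is now unlikely to appear.* Rationale for the Project says that standard infiltration usually lasts only 12 hours. A control arm that loses its effect between 12 and 24 hours would produce an interaction within the retained readings, as the last two table rows show. For VAS, the pilot text has On-Q scoring higher up to 6 hours and the groups similar afterwards. The 6-hour reading is kept, so a VAS interaction could also survive.
- *That omitting 30 minutes favours the liposomal arm.* The pilot does say "The Exparel group demonstrated higher morphine usage at the 30 minute time point", but its early VAS scores were higher with On-Q, so an early VAS reading would have run the other way. Early opioid doses still enter total postoperative use.
- *That restoring the 30-minute reading is the remedy.* The pilot arms already differed there (5.2 against 1.2 mg), so it would not supply a point at which the groups are alike. It would also leave the data-dependent trigger in place.

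The pilot is thin as well: two arms, five On-Q patients, no SDs and no interaction test reported.

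**Conclusion.** The point holds as an internal contradiction with a consequence for the primary analysis. The count, six levels against five scheduled readings, is certain and needs no assumption. So are the absence of any starting reading and of a primary analysis when the interaction is not significant.

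The 94% share describes pilot morphine means only. The power figures are illustrative: about 9-84% if control matches or lies midway between the active arms, and about 81-100% if control follows Exparel to 12 h and On-Q from 24 h. They rest on SD 4.9, compound symmetry, and assumed correlation, group size and control profile. They do not show that the trigger will fail. They show that the documents do not settle whether it fires, so the choice of primary analysis is left to the data.

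**What to change.** In Planned Data Analysis:

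1. Change the within factor to five levels, at 6, 12, 24, 48 and 72 h, so that the interaction has 8 df.
2. Delete the premise of starting comparability and the rule that moves the primary analysis to 72 hours.
3. Name as primary, whatever the interaction shows, the 0-72 h group comparison of the endpoints already defined in Post-operative Protocol: total postoperative opioid use to 72 h, and VAS-R AUC over the five scheduled readings.
4. Make the 72-hour comparison secondary, and report the interaction test descriptively.

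This adds no bedside reading and needs only a change of wording. One consequence should be dealt with at the same time: Sample Size Justification states its morphine difference of 5 and SD of 4.9 for day 3, so the matching values for the 0-72 h total, which the documents do not give, should be stated there.
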